8.11. Withdrawal Due to Adverse Events

Withdrawal due to adverse event should be distinguished from withdrawal due to insufficient response, according to the definition of adverse event noted earlier, and recorded on the appropriate adverse event CRF page.

When a subject withdraws due to a serious adverse event, the serious adverse event must be reported in accordance with the reporting requirements defined below.

8.12. Eliciting Adverse Event Information

The investigator is to report all directly observed adverse events and all adverse events spontaneously reported by the study subject. In addition, each study subject will be questioned about adverse events.

8.13. Reporting Requirements

Each adverse event is to be assessed to determine if it meets the criteria for serious adverse events. If a serious adverse event occurs, expedited reporting will follow local and international regulations, as appropriate.

8.13.1. Serious Adverse Event Reporting Requirements

If a serious adverse event occurs, Pfizer is to be notified within 24 hours of investigator awareness of the event by the investigator. In particular, if the serious adverse event is fatal or life-threatening, notification to Pfizer must be made immediately, irrespective of the extent of available adverse event information. This timeframe also applies to additional new information (follow-up) on previously forwarded serious adverse event reports as well as to the initial and follow-up reporting of Exposure in Utero and exposure via breastfeeding cases.

In the rare event that the investigator does not become aware of the occurrence of a serious adverse event immediately (eg, if an outpatient study subject initially seeks treatment elsewhere), the investigator is to report the event within 24 hours after learning of it and document the time of his/her first awareness of the adverse event.

For all serious adverse events, the investigator is obligated to pursue and provide information to Pfizer in accordance with the timeframes for reporting specified above. In addition, an investigator may be requested by Pfizer to obtain specific additional follow-up information in an expedited fashion. This information may be more detailed than that captured on the adverse event case report form. In general, this will include a description of the adverse event in sufficient detail to allow for a complete medical assessment of the case and independent determination of possible causality. Information on other possible causes of the event, such as concomitant medications and illnesses must be provided. In the case of a subject death, a summary of available autopsy findings must be submitted as soon as possible to Pfizer or its designated representative.

8.13.2. Non-Serious Adverse Event Reporting Requirements

All adverse events will be reported on the adverse event page(s) of the CRF. It should be noted that the form for collection of serious adverse event information is not the same as the adverse event CRF. Where the same data are collected, the forms must be completed in a consistent manner. For example, the same adverse event term should be used on both forms. Adverse events should be reported using concise medical terminology on the CRFs as well as on the form for collection of serious adverse event information.

8.13.3. Sponsor Reporting Requirements to Regulatory Authorities

Adverse event reporting, including suspected serious unexpected adverse reactions, will be carried out in accordance with applicable local regulations.

9. DATA ANALYSIS/STATISTICAL METHODS

Detailed methodology for summary and statistical analyses of the data collected in this trial will be documented in the Statistical Analysis Plan (SAP) and the Statistical Rulebook, which will be dated and maintained by the sponsor, before the time of database release. The reasons for any departure from the planned method of analysis will be fully documented.

9.1. Sample Size Determination

Although analysis for the primary efficacy endpoint will be model based, the sample size calculation is based on a two-sided Chi-Square test with a 0.05 significance level and a 1:1:1 randomization ratio of varenicline 1 mg BID to varenicline 0.5 mg BID to placebo. The study is powered at 80% or greater to detect varenicline (1 mg BID or 0.5 mg BID dose) vs. placebo differences in the CQR from Weeks 9 through 12. The sample size is based on CQR of 9% and 24% for placebo and varenicline respectively, or an odds ratio of 3.2.

A sample size of 300 subjects randomized to varenicline or placebo in a 1:1:1 (100 to varenicline 1 mg BID, 100 to varenicline 0.5 mg BID, 100 to placebo) will provide approximately 80% power to detect a difference in the primary endpoint between varenicline and placebo groups, assuming a true Week 9-12 CQR of 9% and 24% for placebo and varenicline respectively.

Enrollment will be stratified by age group (12-16 vs. 17-19) and sufficient subjects will be enrolled in the 12-16 year old age group to detect a difference in the primary endpoint between varenicline and placebo groups, assuming a true Week 9-12 CQR of 9% and 29% for placebo and varenicline respectively.

In order to ensure sufficient subjects are enrolled in the 12-16 year old stratum, the 17-19 year old stratum will be capped at a maximum of 90 subjects, leaving at least 210 subjects (approximately 70 subjects per treatment group) in the 12-16 year old stratum.

Efficacy Analysis

The primary efficacy inference for the study is a comparison of varenicline to placebo for the CQR for Weeks 9 through 12. This measure will be obtained through reports of cigarette or other nicotine use since the last study visit confirmed by urine cotinine. An exploratory subgroup analysis for each dosing group by weight stratum for the primary endpoint will be provided.

All efficacy analyses will be performed overall as well as on the subgroup of patients who are 12-16 years of age.

Secondary efficacy endpoints are listed in Section [2.2](#).

These efficacy endpoints will be based on subject self-report, with abstinence confirmed by cotinine.

To assess the comparability of subjects across treatment groups, demographic, smoking history, and baseline nicotine dependence and other baseline characteristics will be summarized by treatment group. In addition, subgroup summaries and analyses may be completed, when the number of subjects in the subgroups permits, to evaluate the consistency of the efficacy in the primary and key secondary endpoints over demographic and other baseline characteristics.

Data collected at baseline and other time points will be summarized by treatment group using descriptive statistics. Descriptive statistics, such as the mean, median, standard deviation, and range will be used to summarize continuous variables, and counts and percentages for categorical variables. In addition to tabulated descriptive statistics, graphical data displays may be used to summarize the data.

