9.1.1. Analysis of Primary Endpoint

Logistic regression models will be used in the analyses of primary endpoint. The model will include strata, treatment, and center as independent variables. Treatment by center interaction will be investigated. If the treatment by center interaction is significant in the model containing treatment, center, and treatment by center interaction, then exploratory analyses will be undertaken to explain the nature and source of the interaction. However, the reported p-values will be based on the main effects model.

Additional analyses may be performed adjusting for baseline covariates as additive terms to the primary model, if necessary. Results from any additional analyses will not be used as a substitute for the planned analyses, but may be used as supplemental information for the study report.

Statistical hypotheses for the primary endpoint will be tested in an ordered fashion to preserve overall Type I Error. The 1 mg BID group will be tested against placebo, and if a statistically significant difference is observed, the 0.5 mg BID group will be tested against placebo. A p-value of 0.05 will be considered statistically significant in both tests. Both tests will be presented regardless of the p-value obtained.

The primary efficacy analysis population will be all subjects who took at least 1 dose of randomized study medication (Full Analysis set). Subjects who discontinue the study are assumed to be smokers for the time point of discontinuation through the end of the study. In computing responder rates, subjects who discontinue the study will be included in the denominator but not in the numerator, regardless of their last smoking status evaluation.

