4.2. Statistical Decision Rules

Statistical hypotheses for the primary endpoint will be tested in an ordered fashion to preserve overall Type I Error. The 1 mg BID group will be tested against placebo, and if a statistically significant difference is observed, the 0.5 mg BID group will be tested against placebo. A p-value of 0.05 or smaller will be considered statistically significant in both tests. Both tests will be presented regardless of the p-value obtained.

P-values will be reported with no adjustments for the analysis of multiple secondary endpoints or analyses by strata.

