8.2.3. Primary Efficacy Analysis

The primary efficacy analysis will be analysis of *the 4-week continuous abstinence rate (CAR) from Week 9 through Week 12 of treatment for each varenicline treatment group compared with placebo*.

The 4-week CAR will be summarized by treatment group using descriptive statistics and bar charts.

This will be summarized for the following groups:

- Overall study.
- 12-16 year old age stratum.
- 12-16 year old age stratum, ≤ 55 kg weight stratum.
- 12-16 year old age stratum, > 55 kg weight stratum.
- 17-19 year old age stratum.

The 4-week CAR will be analyzed using a logistic regression model as described in [Section 8.1.1.2](#). Odds ratios and 95% confidence intervals will be shown in plots.

These will be analysed for the following groups:

- Overall study.
- 12-16 year old age stratum (without age strata covariate).
- 12-16 year old age stratum, ≤ 55 kg weight stratum (without age strata or body weight strata covariates).
- 12-16 year old age stratum, > 55 kg weight stratum (without age strata or body weight strata covariates).

While the analysis will be performed for sets listed above, the primary analysis of the primary efficacy endpoint is the overall study.

Statistical hypotheses for the primary endpoint will be tested in an ordered fashion to preserve overall Type I Error. The 1 mg BID group will be tested against placebo, and if a statistically significant difference is observed, the 0.5 mg BID group will be tested against placebo. A p-value of 0.05 will be considered statistically significant in both tests. Both tests will be presented regardless of the p-value obtained.

A sensitivity analysis excluding site **PPD** will be performed based on the primary analysis of the primary endpoint. This site was terminated based on concerns regarding GCP non-compliance.

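### The stated power of 80% or more holds for each dose taken alone; under the ordered testing rule the chance of a formal 0.5 mg BID claim is about 70% to 73%

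*Protocol*

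**What the plan says.** Protocol Section 9.1 sets out the sample size as follows.

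- **Method:** "the sample size calculation is based on a two-sided Chi-Square test with a 0.05 significance level".
- **Rates:** "The sample size is based on CQR of 9% and 24% for placebo and varenicline respectively, or an odds ratio of 3.2". There is one varenicline rate, not one per dose.
- **Arms:** "100 to varenicline 1 mg BID, 100 to varenicline 0.5 mg BID, 100 to placebo".
- **Power:** "The study is powered at 80% or greater to detect varenicline (1 mg BID or 0.5 mg BID dose) vs. placebo differences". The next paragraph says that 300 subjects "will provide approximately 80% power to detect a difference in the primary endpoint between varenicline and placebo groups".

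Protocol 9.1.1 gives the decision rule for the primary endpoint. The 1 mg BID group is compared with placebo first, and "if a statistically significant difference is observed, the 0.5 mg BID group will be tested against placebo". Each step uses 0.05. SAP 4.2 repeats the rule and its purpose: "Statistical hypotheses for the primary endpoint will be tested in an ordered fashion to preserve overall Type I Error". SAP 8.2.3 repeats it again and adds: "Both tests will be presented regardless of the p-value obtained". SAP 4.1 lists 0.5 mg BID against placebo as one of the two primary hypotheses.

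Neither document gives a power figure for the second step under this rule.

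**The concern.** The power sentence names both doses, but it is worked out as if each comparison stood alone. Under a fixed sequence that is true only of the dose tested first. A 0.5 mg BID result counts formally only when 1 mg BID has also succeeded, so the relevant probability is that of both tests being significant, which is lower than the power of either.

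Someone who reads Section 9.1 by itself would take 80% as the chance of a confirmatory finding for 0.5 mg BID too. If the trial then gave no formal 0.5 mg BID result, that could be read as a failure despite 80% power, when the design offered less at its own planning rates.

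**Working it through.** **Inputs** (all from Protocol 9.1 and 9.1.1): n = 100 per arm; placebo rate p0 = 0.09; varenicline rate p1 = 0.24, used for both doses because only one rate is given; two-sided alpha 0.05; uncorrected chi-square test. Discontinued subjects count as smokers and stay in the denominator, so n remains 100.

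**1. Reproduce the plan's figure (one dose against placebo).**

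- Odds ratio: (0.24/0.76) / (0.09/0.91) = 3.19, matching the stated 3.2.
- Pooled rate: (0.09 + 0.24)/2 = 0.165. Null standard error: √(2 × 0.165 × 0.835 / 100) = 0.0525.
- Standard error under the alternative: √((0.09 × 0.91 + 0.24 × 0.76)/100) = √(0.2643/100) = 0.0514.
- Power: Φ[(0.15 − 1.96 × 0.0525)/0.0514] = Φ(0.916) = **82.0%**.
- Exact enumeration of the chi-square test over the binomial outcomes: **83.5%**.

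By the normal approximation 95 per arm suffice for 80%, so the stated power is met with 100.

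**2. Apply the ordered rule.** A formal 0.5 mg BID claim requires both tests to be significant in favour of varenicline. The tests share the placebo arm and are therefore correlated:

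ρ = p0(1 − p0) / [p0(1 − p0) + p1(1 − p1)] = 0.0819 / 0.2643 = 0.310.

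- Bivariate normal, both limits at 0.916, ρ = 0.310: **69.7%**.
- Exact enumeration over three independent binomials (0.09, 0.24, 0.24): **0.7335, or 73.4%**. A simulation of 2,000,000 trials gave 0.7339.

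**3. Related probabilities from the same enumeration.**

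| Event | Probability |
|---|---|
| 1 mg BID significant | 0.8350 |
| 0.5 mg BID significant, ignoring the order | 0.8350 |
| Both significant (formal 0.5 mg BID claim) | 0.7335 |
| 0.5 mg BID significant but not claimable | 0.8350 − 0.7335 = 0.1015 |
| At least one dose significant | 0.9366 |
| 0.5 mg BID significant, given that 1 mg BID is | 0.7335/0.8350 = 0.878 |

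**4. Sensitivity to the form of the test.** The documents do not say whether the chi-square is continuity-corrected. The corrected version gives 77.3% alone and 64.5% for both; Fisher's test gives 78.5% and 66.5%. Neither reaches the stated 80% for one comparison, so the uncorrected test, which favours the plan, is used here.

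**5. Sensitivity to equal rates.** Placebo is held at 9% and the chi-square is enumerated exactly. The unequal rates are assumptions for illustration and are not in the documents.

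| 1 mg BID | 0.5 mg BID | 0.5 mg BID alone | Both |
|---|---|---|---|
| 24% | 24% | 83.5% | 73.4% |
| 28% | 24% | 83.5% | 80.9% |
| 30% | 24% | 83.5% | 82.3% |
| 24% | 20% | 61.2% | 56.0% |
| 24% | 18% | 46.9% | 43.9% |

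**The case against.** The strongest reply is that nothing in Section 9.1 is false. The sentence joins the doses with an *or* and rests on a two-group test. Read per comparison, as at least one dose, or as 0.5 mg BID given success at 1 mg BID, it stays above 80% (82.0% to 83.5%, 93.7% and 87.8%). Only the joint probability falls short, and the plan never claims it. The ordered rule sits in a subsection of the same Section 9.1, and sizing on single comparisons before testing in sequence is coherent.

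Much of this stands: the arithmetic is sound and the Type I error is properly controlled. It does not close the gap. The at-least-one reading does not fit a stated power of approximately 80%. The per-comparison and conditional readings do not answer how likely a formal 0.5 mg BID result is, and that is a primary hypothesis.

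A second reply is that 70% to 73% depends on equal rates. That is true: the table above runs from 44% to 82%. If 1 mg BID did better than 24%, the 0.5 mg BID claim could reach 80%. But equality is what the protocol's single rate implies, and the restated text should carry it as a condition.

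A third is that little follows in practice, because both p-values are reported anyway. That limits the harm. A reported p-value is still not a formal claim under a rule adopted to protect the error rate.

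**Conclusion.** The concern holds. The stated power is correct for each dose against placebo taken alone and for 1 mg BID, which is tested first. It does not hold for a formal 0.5 mg BID claim, whose probability at the planning rates is 69.7% to 73.4%, some 7 to 10 points below 80%. In about 10% of trials 0.5 mg BID would be nominally significant but not claimable.

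This rests on 100 per arm, 9% against 24% for both doses, and the uncorrected chi-square. The strata and center terms of the planned logistic model are not represented, as in the protocol's own calculation. The range 70% to 73% reflects only the method of calculation; different true rates for the two doses would move the figure further. Power for 1 mg BID and the Type I error are unaffected. This is a gap in the stated power, not a flaw in the test procedure.

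**What to change.** Restate the power in Protocol 9.1, for example:

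> With 100 subjects per arm and rates of 9% and 24%, each dose-versus-placebo comparison taken alone has about 82% (normal approximation) to 83.5% (exact enumeration of the uncorrected chi-square test) power; this applies to 1 mg BID. Under the ordered procedure in Section 9.1.1, the probability of formally declaring 0.5 mg BID effective is about 70% to 73% by the same methods, if both doses have a 24% rate.

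The cost is two sentences. Sample size, alpha, test order, model and decision rule do not change, and no extra subjects are needed. The downside for the sponsor is a less favourable stated power for 0.5 mg BID. For scale only, about 115 per arm would give 80% for both tests (80.1% by exact enumeration); that increase is not proposed.

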9.1.1. Analysis of Primary Endpoint

Logistic regression models will be used in the analyses of primary endpoint. The model will include strata, treatment, and center as independent variables. Treatment by center interaction will be investigated. If the treatment by center interaction is significant in the model containing treatment, center, and treatment by center interaction, then exploratory analyses will be undertaken to explain the nature and source of the interaction. However, the reported p-values will be based on the main effects model.

Additional analyses may be performed adjusting for baseline covariates as additive terms to the primary model, if necessary. Results from any additional analyses will not be used as a substitute for the planned analyses, but may be used as supplemental information for the study report.

Statistical hypotheses for the primary endpoint will be tested in an ordered fashion to preserve overall Type I Error. The 1 mg BID group will be tested against placebo, and if a statistically significant difference is observed, the 0.5 mg BID group will be tested against placebo. A p-value of 0.05 will be considered statistically significant in both tests. Both tests will be presented regardless of the p-value obtained.

The primary efficacy analysis population will be all subjects who took at least 1 dose of randomized study medication (Full Analysis set). Subjects who discontinue the study are assumed to be smokers for the time point of discontinuation through the end of the study. In computing responder rates, subjects who discontinue the study will be included in the denominator but not in the numerator, regardless of their last smoking status evaluation.

9.1.2. Analysis of Secondary Endpoints

9.1.2.1. Efficacy Endpoints

There are several secondary smoking abstinence endpoints for this study, as indicated in Section 2.2. Each of these binary secondary endpoints will be analyzed using procedures similar to that described above for the primary efficacy endpoint. All statistical tests will be two-sided and at a 0.05 level of significance. P-values will be reported with no adjustments for the analysis of multiple secondary endpoints.

The number of cigarettes smoked over the past seven days will be collected by completion of the NUI at each visit. The reduction in the number of the cigarettes smoked will be calculated at each visit by subtracting the reported number of cigarettes smoked in the past 7 days at each visit from the number of cigarettes smoked in the past 7 days reported at the baseline visit. Longitudinal repeated measures models including strata, treatment, center,

and baseline number of cigarettes smoked will be used to assess the effect of treatment on the reduction in the number of cigarettes smoked.

Pharmacokinetic Endpoints

The plasma concentration-time data collected in this study will be analyzed via nonlinear mixed effects (NONMEM software) to describe the population pharmacokinetics (PK) of varenicline including an assessment of covariate effects in adolescent smokers.

Varenicline exposure data derived from the individual Bayesian estimates of the pharmacokinetic parameters will be subsequently utilized to characterize the population exposure-response relationships for selected measures of efficacy and safety/tolerability of varenicline in this pediatric population. Model development may require the use of data from previous clinical studies. An analysis plan describing the details of the model building, covariate assessment and model validation will be provided separately before the unblinding of the data.

9.2. Safety Analysis

All safety analyses will be performed overall as well as on the subgroup of patients who are 12-16 years of age. Laboratory and other safety data will be subjected to clinical review and summarized, using Pfizer Data Standards, by frequencies of events and mean changes from Baseline.

The following summaries will be used to assess the safety of subjects in this study:

- Incidence and type of AEs;
- Incidence and type of SAEs;
- Change from baseline in laboratory parameters;
- Incidence of clinically significant laboratory parameters;
- Change from baseline in vital signs;
- Incidence of clinically significant vital sign parameters;
- Frequency and percent of subjects endorsing suicidal ideation or behavior.

All safety analyses will use the population of all subjects who received at least 1 dose of study drug.

In addition to the standard safety summaries for the vital signs data collected at each visit, the change from Baseline in BMI at Week 12 will be summarized by treatment group. Change from Baseline in BMI and any other safety endpoints of interest may be summarized for subgroups of interest if the number of subjects in the subgroup permits.

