- Ask subject to recall the times of last 2 doses of trial medications and record this information in the dosing log;
- At Week 12 or ET12 only, record height and weight;

The following additional activity will be conducted at Visit Weeks 9-12, and at Early Termination:

- Urine cotinine test at site;

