7.2.3. Physical Examinations

A physical examination including height and weight will be performed at screening visit by trained medical personnel. Height and weight will be collected again at Baseline and at the Week 12 end-of-treatment visit or early termination if prior to Week 12. Height and weight must be measured at least three times. Weight should be obtained with a calibrated scale and height should be measured with a stadiometer.

CDC growth charts will be provided to investigators to record height and weight.

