6.3. Windowing and Time Point Assignments

No windows will be used to determine planned weeks and days for this study. All analyses will be based on nominal day and week as recorded on the CRF. The exception will be the early termination visit. This visit will be assigned a nominal week according to the following windowing algorithm. (Note: The count of days starts from the first day of dosing and all intervals below are inclusive of the end days):

Week 1: day 2 through 10
Week 2: day 11 through 17
Week 3: day 18 through 24
Week 4: day 25 through 31
Week 5: day 32 through 38
Week 6: day 39 through 45
Week 7: day 46 through 52
Week 8: day 53 through 59
Week 9: day 60 through 66
Week 10: day 67 through 73
Week 11: day 74 through 80
Week 12: day 81 through 87
Week 13: day 88 through 94
Week 14: day 95 through 101
Week 15: day 102 through 108
Week 16: day 109 through 126
Week 20: day 127 through 147
Week 22: day 148 through 161
Week 24: day 162 through 182
Week 28: day 190 through 210
Week 32: day 218 through 238
Week 36: day 246 through 266
Week 40: day 274 through 294
Week 44: day 302 through 322
Week 48: day 330 through 350
Week 52: day 358 on

In the event of ties, the non “early termination” visit (i.e. the earlier visit) will be selected as the representative visit.

Day will be computed by subtracting the date of the first dose of study medication from the date of the evaluation. In order that the first day of dosing be defined as Day 1, one day will be added to this difference.

Baseline will be defined as the latest evaluation performed prior to the first dose of study medication.

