8.2.6.2. Clinical Laboratory Measures

Laboratory abnormalities will be summarized by treatment group according to the following three baseline statuses: Normal Baseline, Abnormal Baseline, and Without Regard to Baseline. Median change from baseline to final observed laboratory data will also be summarized by treatment group. Shift tables from baseline to each assessment will be provided by treatment group.

[REDACTED]

These will be summarized for the following groups:

- Overall study
- 12-16 year old age stratum
- 12-16 year old age stratum, ≤ 55 kg weight stratum
- 12-16 year old age stratum, > 55 kg weight stratum
- 17-19 year old age stratum

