8.2.6.4. Height and Weight

As this is a study of adolescents who may still be growing, height will be measured at baseline and Week 12 (or end of treatment) in addition to weight. Descriptive statistics will be presented by treatment group and for height, weight, and body mass index (BMI) at baseline and Week 12. In addition, summary statistics for change from baseline to Week 12 will be displayed for each measure. Multiple measurements repeated at a given visit will be summarized by the mean of the repeated values.

These will be summarized for the following groups:

- Overall study
- 12-16 year old age stratum
- 12-16 year old age stratum, ≤ 55 kg weight stratum

- 12-16 year old age stratum, >55 kg weight stratum
- 17-19 year old age stratum

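### Under the SAP 6.3 windows, a height and weight taken at early termination before day 81 enters no planned height, weight or BMI change summary

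*Protocol*

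**What the plan says.** **Collection.** Protocol Table 1 schedules height and weight at screening, baseline, Week 12 and ET12. Protocol 6.2.2 says "At Week 12 or ET12 only, record height and weight", and Protocol 7.2.3 places the post-baseline measurement "at the Week 12 end-of-treatment visit or early termination if prior to Week 12".

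**Summary.** In Protocol 9.2, "the change from Baseline in BMI at Week 12 will be summarized by treatment group". SAP 8.2.6.4 plans descriptive statistics for height, weight and BMI at baseline and Week 12, and adds that "summary statistics for change from baseline to Week 12 will be displayed for each measure". The same paragraph opens by saying that "height will be measured at baseline and Week 12 (or end of treatment) in addition to weight".

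**Time-point rule.** SAP 6.3 analyses all visits by the nominal week on the CRF, with early termination as the one exception: "This visit will be assigned a nominal week according to the following windowing algorithm". The relevant entry is "Week 12: day 81 through 87"; the windows before it run from day 2 to day 80 and carry the labels Week 1 to Week 11.

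**Population.** Protocol 9.2 and SAP 8.2.6 define the safety population as everyone who received at least one dose. SAP 7 gives no missing-data rule for height, weight or BMI.

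**The concern.** For a subject who leaves the study early, the ET12 value is the only post-baseline height and weight there will be. The protocol requires it, but the stated rules then place most such values in weeks for which no height, weight or BMI summary is planned. The Week 12 table would cover fewer subjects than the safety population, and the plan neither says so nor offers a companion summary.

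Other repeated numeric safety measures in this SAP keep early leavers in view. For laboratory data, "Median change from baseline to final observed laboratory data will also be summarized by treatment group" (SAP 8.2.6.2). Vital signs are described at every available visit (SAP 8.2.6.3). HADS has change at each visit, the maximum on-treatment increase and a shift to the worst post-baseline score (SAP 8.2.6.7). Height, weight and BMI are tied to one week.

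At stake is how completely the trial describes weight and growth in adolescents, in a study whose primary objective includes safety and tolerability. There is also a programming risk: two programmers could build different Week 12 tables from the same text.

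**Working it through.** The plan states no figure on this point, so there is none to reproduce. The check applies the rules as written and then gives the scale under labelled assumptions.

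**Step 1. Apply the SAP 6.3 windows to an ET12 visit.**

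| Study day of ET12 | Window | Label | Change summary planned in SAP 8.2.6.4? |
|---|---|---|---|
| 40 | 39–45 | Week 6 | No |
| 80 | 74–80 | Week 11 | No |
| 81 | 81–87 | Week 12 | Yes |
| 84 | 81–87 | Week 12 | Yes |

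Days 2 to 80 (80 − 2 + 1 = 79 days) map to Weeks 1 to 11. Days 81 to 87 map to Week 12. The 79 counts calendar days, not subjects, and says nothing about how many people leave.

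**Step 2. Who is affected.** Only subjects who leave the study before day 81 and attend ET12. Protocol 6.4 lets subjects who stop drug remain on the visit schedule and encourages them to do so; they can give a Week 12 weight. Subjects who leave and do not attend ET12 have no value to recover under any rule.

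**Step 3. Effect on an arm mean.** Among subjects with a post-baseline weight, let d be the share whose only value precedes day 81. Let S be the mean change in subjects measured at Week 12 and L the mean change in the early leavers.

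- Mean over all measured subjects = (1 − d)S + dL
- Week 12 mean minus that mean = S − (1 − d)S − dL = d(S − L)

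The documents give neither d nor S − L. Assumed values, in kg:

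| d | S − L of 0.5 | S − L of 1 | S − L of 2 |
|---|---|---|---|
| 10% | 0.05 | 0.10 | 0.20 |
| 20% | 0.10 | 0.20 | 0.40 |
| 30% | 0.15 | 0.30 | 0.60 |
| 40% | 0.20 | 0.40 | 0.80 |

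The table shows absolute size; the sign is that of S − L, which is unknown.

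**Step 4. Effect on a difference between arms.** The error is d(S − L) in the drug arm minus d(S − L) in the placebo arm. With d = 20% and S − L = 1 kg in both arms, it is 0.20 − 0.20 = 0. With the same drug-arm values and no gap on placebo, it is 0.20 − 0 = 0.20 kg. The result therefore depends on how the arms differ, which the documents do not tell us.

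**Step 5. Numbers of subjects.** Protocol 9.1 plans 100 per arm. If 10%, 20%, 30% or 40% leave before day 81 and the rest attend Week 12, the Week 12 summary holds 90, 80, 70 or 60 per arm. A last-value summary could recover at most 10, 20, 30 or 40, and only if every leaver attends ET12. Protocol 6.4 requests a final visit where applicable and foresees loss to follow-up, so these are upper limits.

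**The case against.** **The SAP may already mean an end-of-treatment column.** Only one treatment-phase weight is planned after baseline, and SAP 8.2.6.4 begins by naming end of treatment as an alternative to Week 12. The later mentions of Week 12 could be shorthand for that single value. This stands as a possible reading. It does not remove the point: the phrase describes when the measurement is taken, the two summary sentences name Week 12 alone, and 6.3 would still label a day 40 visit Week 6. The text needs to say which rule governs.

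**The laboratory comparison proves little.** Laboratory tests are drawn several times, so a final-value rule is needed to choose among them. That is fair. The vital signs and HADS comparisons remain, since their summaries by visit also retain early leavers.

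**A fixed Week 12 summary is legitimate.** It is, because it holds treatment duration nearly constant. The proposal keeps it.

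**The consequence is small.** There is no formal inference on safety, and nausea and vomiting are captured as adverse events in all dosed subjects whether or not they leave. This stands and limits the weight of the point.

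**A stronger reading.** A reader might infer that the omission flatters varenicline, since subjects who leave because of nausea or vomiting would be the ones losing weight. The documents do not support this. Protocol 1.2 reports more nausea and vomiting on drug in the two-week adolescent study, but also that nobody in it discontinued or had a dose reduction for an adverse event. It describes adult nausea as generally mild or moderate and often transient. Nothing in the documents links these events to weight loss or to leaving the study.

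**Conclusion.** The gap is real but modest. On the literal rules, the only post-baseline height and weight of a subject who leaves the study before day 81 enters no planned height, weight or BMI change summary. It enters only if SAP 8.2.6.4 is read as an end-of-treatment column, and that reading conflicts with SAP 6.3.

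A reader might infer that every ET12 weight is lost, or that subjects who stop drug drop out of the table. Neither follows: early termination visits on days 81 to 87 count as Week 12, and subjects who stop drug but keep attending can still supply a Week 12 value.

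The size is d(S − L) within an arm. The range of 0.05 to 0.8 kg rests wholly on assumed shares of 10% to 40% and assumed differences of 0.5 to 2 kg. The direction is not established, and the error in an arm difference may be zero. The summary is descriptive, and no primary inference depends on it. The change is worth making because it is cheap and uses measurements already required.

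**What to change.** In SAP 8.2.6.4, with matching words in Protocol 9.2, add change from Baseline to the last treatment-period measurement of height, weight and BMI (Week 12 or ET12, whichever the subject has). Include all safety-set subjects with a post-baseline value, by arm and by the strata already listed. Show n and the time of measurement for each arm. Keep the Week 12 summary beside it, and state that ET12 values before day 81 are excluded from the Week 12 column and included in the added one. That also settles the conflict with SAP 6.3.

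The cost is a wording change and one further column in an existing table, with no new data. The downside is that the added column mixes treatment durations, which is why the Week 12 summary stays and the time of measurement is reported.
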